#### **Interim Analysis**

There will not be any interim analysis given the low risk profile of the study formulation.

### **7.3 Subject Population(s) for Analysis**

Each participant who received the study drug will be included in the primary analysis regardless of study withdrawal for any reason. In the event of any study withdrawals, in secondary analysis we will examine the sensitivity of our results to the exclusion of patients who withdrew.

## 8 Safety and Adverse Events

### 8.1 Definitions

#### Unanticipated Problems Involving Risk to Subjects or Others (UPIRTSO)

Any unanticipated problem or adverse event that meets the following three criteria:

- Serious: Serious problems or events that results in significant harm, (which may be physical, psychological, financial, social, economic, or legal) or increased risk for the subject or others (including individuals who are not research subjects). These include: (1) death; (2) life threatening adverse experience; (3) hospitalization - inpatient, new, or prolonged; (4) disability/incapacity - persistent or significant; (5) birth defect/anomaly; (6) breach of confidentiality and (7) other problems, events, or new information (i.e. publications, DSMB reports, interim findings, product labeling change) that in the opinion of the local investigator may adversely affect the rights, safety, or welfare of the subjects or others, or substantially compromise the research data, **AND**
- Unanticipated: (i.e. unexpected) problems or events are those that are not already described as potential risks in the protocol, consent document, not listed in the Investigator's Brochure, or not part of an underlying disease. A problem or event is "unanticipated" when it was unforeseeable at the time of its occurrence. A problem or event is "unanticipated" when it occurs at an increased frequency or at an increased severity than expected, **AND**
- Related: A problem or event is "related" if it is possibly related to the research procedures.

#### Adverse Event

An AE is defined as any untoward medical occurrence in a patient administered a pharmaceutical product and which does not necessarily have a causal relationship with the treatment. An AE can therefore be any unfavorable and unintended sign (including an abnormal lab finding), symptom or disease temporally associated with the use of a medicinal product, whether or not related to the medicinal product.

Each AE must be assessed by the investigator as to whether or not there is a reasonable possibility of causal relationship to Valchlor, and documented as either related or unrelated. The determination of the likelihood that Valchlor caused the AE must be provided by an investigator who is a qualified physician. .

Initial screening for AE will include non-directed questioning of the patient at each follow-up visit during the study period along with the directed questioning and examination regarding:

- Signs and symptoms of idiosyncratic allergic contact dermatitis

Patients will be instructed to stop using Valchlor and to contact the study coordinator if swelling and blistering occurs as this may represent early signs of allergic contact dermatitis. The primary investigator will then evaluate the patient and if the signs and symptoms are

compatible with allergic contact dermatitis, the patient will be offered treatment using a medium-potency topical corticosteroid to involved areas in the AM, with resumption of Valchlor application in the PM. Patients with persistent allergic contact dermatitis reactions unable to be managed as outlined above will exit the study.

- Unintentional mucosal and/ocular exposure

Patients will be warned not to apply Valchlor near eyes, mouth, or nose as it can cause pain, redness, swelling, burning, sensitivity to light, blurred vision, and blindness or permanent eye injury. If accidental Valchlor exposure to nose, mouth or eyes occurs, patients will be instructed to rinse affected areas with large amounts of water for 15 minutes and to contact the study coordinator. The primary investigator will then contact the patient to review application site instructions and schedule a follow-up evaluation if the patient reports persistent symptoms or erythema.

### **Serious Adverse Event**

Adverse events defined as serious will be the following:

- death
- life threatening adverse experience
- hospitalization
- inpatient, new, or prolonged; disability/incapacity
- persistent or significant disability or incapacity
- birth defect/anomaly
- medically significant

Medically Significant: refers to important medical events that may not immediately result in death, be life-threatening, or require hospitalization but may be considered to be SAEs when, based upon appropriate medical judgment, they may jeopardize the subject, and may require medical or surgical intervention to prevent one of the outcomes listed in the definitions above.

All adverse events that do not meet any of the criteria for serious, will be regarded as **non-serious adverse events**.

### **Adverse Event Reporting Period**

For this study, the study treatment follow-up period is defined as the last scheduled visit.

### **Preexisting Condition**

A preexisting condition is one that is present at the start of the study. A preexisting condition will be recorded as an adverse event if the frequency, intensity, or the character of the condition worsens during the study period.

### **General Physical Examination Findings**

At screening, any clinically significant abnormality should be recorded as a preexisting condition. At the end of the study, any new clinically significant findings/abnormalities that meet the definition of an adverse event will also be recorded and documented as an adverse event.

**Post-study Adverse Event**

All unresolved adverse events should be followed by the sponsor-investigator until the events are resolved, the subject is lost to follow-up, or the adverse event is otherwise explained. At the last scheduled visit, the sponsor-investigator should instruct each subject to report, to the sponsor-investigator, any subsequent event(s) that the subject, or the subject's personal physician, believes might reasonably be related to participation in this study.

**Abnormal Laboratory Values**

Any clinical laboratory abnormality that can reasonably be related to the topical administration of Valchlor should be documented as an adverse event.

**Hospitalization, Prolonged Hospitalization or Surgery**

Hospitalization, prolonged hospitalization, or surgery is to be reported as an adverse event if it can reasonably be related to the topical use of Valchlor.

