**8.2 Recording of Adverse Events**

At each contact with the subject, the study team will seek information on adverse events by specific questioning and, as appropriate, by examination. Information on all adverse events should be recorded immediately in the source document, and also in the appropriate adverse event section of the case report form (CRF). All clearly clinically related signs, symptoms, and abnormal diagnostic, laboratory or procedure results will be recorded in the source document.

All adverse events occurring during the study period will be recorded. The clinical course of each event should be followed until resolution, stabilization, or until it has been ultimately determined that the study treatment or participation is not the probable cause. Serious adverse events that are still ongoing at the end of the study period must be followed up, to determine the final outcome. Any serious adverse event that occurs during the Adverse Event Reporting Period and is considered to be at least possibly related to the study treatment or study participation should be recorded and reported to Actelion immediately (see 8.3 below).

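### Section 8.1 puts relatedness to Valchlor into the test for documenting or reporting laboratory abnormalities, hospitalizations and surgery as adverse events, in conflict with its own causality-free definition

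*Combined protocol and SAP*

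**What the plan says.** All of the following is in section 8 of the combined protocol and SAP.

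- **8.1, Adverse Event.** The definition takes in any untoward occurrence, names abnormal laboratory findings expressly, and ends with "symptom or disease temporally associated with the use of a medicinal product, whether or not related to the medicinal product". Causality is a second step: each AE is assessed by the investigator and "documented as either related or unrelated".
- **8.1, Serious Adverse Event.** The list opens "Adverse events defined as serious will be the following" and includes hospitalization, with no relatedness condition.
- **8.1, Abnormal Laboratory Values.** The rule reads "Any clinical laboratory abnormality that can reasonably be related to the topical administration of Valchlor should be documented as an adverse event".
- **8.1, Hospitalization, Prolonged Hospitalization or Surgery.** For all three, "surgery is to be reported as an adverse event if it can reasonably be related to the topical use of Valchlor" is how the sentence ends.
- **8.2, Recording of Adverse Events.** "All adverse events occurring during the study period will be recorded".
- **8.6, Medical Monitoring.** The principal investigator's oversight includes a regular look at how many SAEs there are and of what type.

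**The concern.** The general definition and the two specific paragraphs give different answers for the same event. A hospitalization that the investigator judges unrelated is covered by the definition, but it fails the condition in the paragraph written for hospitalizations. A coordinator with such a case will naturally turn to that paragraph.

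What is at stake is the completeness of the all-cause AE and SAE record. The study is open-label with a single arm (sections 5.3 and 5.8), so there is no control group against which to check individual attributions. Section 1.6 itself says that the skin-cancer risk directly attributable to Valchlor has not been established, so for one named risk the protocol treats attribution as unsettled. There is no interim analysis (section 7.2), and contact dermatitis is the only trigger named in the stopping rules (section 8.5). The SAE review in section 8.6 is therefore the main place where an unexpected pattern would be noticed.

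**Working it through.** The plan gives no figure on this point, so there is none to reproduce. The check is mainly textual.

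**Step 1: compare the rules.**

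| Place | Subject | Relatedness condition? |
|---|---|---|
| 8.1 Adverse Event | Any untoward occurrence, including laboratory findings | No; assessed afterwards |
| 8.1 Serious Adverse Event | Hospitalization as a seriousness criterion | No |
| 8.1 General Physical Examination Findings | New end-of-study findings that meet the AE definition | No |
| 8.1 Abnormal Laboratory Values | Laboratory abnormality | Yes |
| 8.1 Hospitalization, Prolonged Hospitalization or Surgery | Hospitalization, surgery | Yes |
| 8.2 Recording | All AEs | No |
| 8.3.1 AE form | Has a field for relationship to the research | No; the field presupposes that unrelated events are entered |

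The clash is most direct for laboratory findings, which the definition includes without condition and the later paragraph conditions.

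**Step 2: ask whether another rule settles it.** The recording rule in 8.2 and the end-of-study rule both apply to events that are AEs, and what counts as an AE is the disputed point. SAEs are defined as a subset of AEs, so an event excluded as an AE is also excluded as an SAE and drops out of the count in 8.6. No sentence ranks the general definition above the specific paragraphs, or the reverse.

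**Step 3: direction and possible size.** A relatedness filter can only lower the all-cause count or leave it unchanged. For scale, let n = 20 (section 3.2), let h be the proportion of patients with a hospitalization or surgery from any cause, and let r be the share judged related. Neither h nor r is in the documents; both are assumed here. The filter is taken as strictly applied, with the underlying illness not otherwise entered. Then

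P(at least one counted) = 1 − (1 − h·r)^20, with r = 1 giving the all-cause value.

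| Assumed h | Expected patients, 20·h | r = 1 | r = 0.5 | r = 0.25 | r = 0 |
|---|---|---|---|---|---|
| 2% | 0.4 | 0.33 | 0.18 | 0.10 | 0 |
| 5% | 1.0 | 0.64 | 0.40 | 0.22 | 0 |
| 10% | 2.0 | 0.88 | 0.64 | 0.40 | 0 |

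For example, with h = 5% and r = 0.5: 1 − (1 − 0.025)^20 = 0.40, against 1 − 0.95^20 = 0.64 with no filter. The effect runs from none (all judged related) to complete loss (none judged related), so the table illustrates the mechanism and does not estimate its size.

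**The case against.** The strongest reply is that the two paragraphs need not exclude anything. They say if, not only if. The laboratory sentence gives a sufficient condition and is silent on other abnormalities. The hospitalization sentence speaks of reporting, and elsewhere (8.2, 8.3 and 8.3.2) the protocol limits reports to the manufacturer by relatedness while recording all AEs. Further, the sentence conditions the hospitalization or operation, not the illness behind it. An unrelated pneumonia is still an untoward occurrence under the definition and would ordinarily be recorded under 8.2. Interval changes in medical history also go on the case report form (section 3.7) and are reviewed at weeks 12 and 24, so such events could be checked against the AE log.

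Much of this stands, and it rules out several stronger readings that a reader might infer:

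- *These events are AEs only if judged related.* That is one reading of the two paragraphs; it requires them to override the definition.
- *Unrelated events vanish before anyone can count them.* The interval history and the general recording rule make that unlikely as a general outcome.
- *The safety result is biased downward.* The primary safety endpoint concerns the days between unintentional mucosal or ocular exposures (section 3.6), which this wording does not touch, and section 7 plans no AE-rate estimate.
- *One dropped event moves the exact two-sided 95% upper limit from 24.9% (1/20) to 16.8% (0/20).* The arithmetic is right, but it holds for any single miscounted event and bounds a rate that the plan never estimates.

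The laboratory paragraph also has little practical reach, since the only scheduled laboratory test is the urine pregnancy test (section 6).

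The reply does not remove the conflict. The reporting reading is possible but nowhere stated, and the laboratory sentence says documented, not reported. 8.2 adds to the doubt by saying that possibly related SAEs should be both recorded and reported.

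**Conclusion.** The inconsistency is real and should be corrected. The two paragraphs put relatedness into the test for documenting or reporting an AE, against the definition in the same section, and nothing in the protocol resolves the conflict. Followed literally, they could drop unrelated-judged hospitalizations and surgery from the all-cause AE record, and unrelated-judged hospitalizations from the SAE count reviewed under section 8.6.

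This is a possible undercount. Its direction is known, downward or nil, but its size is not derivable from the documents. It depends on how staff read the paragraphs, on how many such events occur among 20 patients, and on what share is judged unrelated. No endpoint or analysis specified in sections 3 or 7 is shown to be affected.

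**What to change.** Delete the relatedness condition from the two paragraphs of section 8.1, so that recording comes first and attribution second:

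- **Abnormal Laboratory Values:** every clinically significant laboratory abnormality is recorded as an AE and then classified as related or unrelated.
- **Hospitalization, Prolonged Hospitalization or Surgery:** every hospitalization, prolongation or operation arising from an untoward medical occurrence is recorded as an AE and then classified in the same way. Planned procedures for stable pre-existing conditions stay outside, consistent with the Preexisting Condition paragraph, which records such a condition only when it worsens. Without that limit the change would create a new conflict.

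Leave the expedited reporting of possibly related SAEs to the manufacturer (sections 8.2, 8.3 and 8.3.2) unchanged; filtering those reports by relatedness is a separate matter and does not contradict the definition.

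The cost is two sentences of protocol wording and a few more AE entries. No visit, test or treatment rule changes.

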**8.2 Recording of Adverse Events**

At each contact with the subject, the study team will seek information on adverse events by specific questioning and, as appropriate, by examination. Information on all adverse events should be recorded immediately in the source document, and also in the appropriate adverse event section of the case report form (CRF). All clearly clinically related signs, symptoms, and abnormal diagnostic, laboratory or procedure results will be recorded in the source document.

All adverse events occurring during the study period will be recorded. The clinical course of each event should be followed until resolution, stabilization, or until it has been ultimately determined that the study treatment or participation is not the probable cause. Serious adverse events that are still ongoing at the end of the study period must be followed up, to determine the final outcome. Any serious adverse event that occurs during the Adverse Event Reporting Period and is considered to be at least possibly related to the study treatment or study participation should be recorded and reported to Actelion immediately (see 8.3 below).

**8.3 Reporting of Serious Adverse Events and Unanticipated Problems**

When an adverse event has been identified, the study team will take appropriate action necessary to protect the study participant and then complete the Study Adverse Event Worksheet and log. The sponsor-investigator will evaluate the event and determine the necessary follow-up and reporting required. All SAEs considered possibly as related to study medication by the Sponsor-Investigator must be reported immediately to Actelion Global Drug Safety (GDS) as set forth in the IIS agreement (on Actelion SAE template FRM-001093). Actelion reserves the right to request additional information and clarifications on cases forwarded by the Sponsor-Investigator.

North America (US and Canada)  
San Francisco, USA  
[contact]  
[contact]

### **8.3.1 Sponsor-Investigator reporting: notifying the Mayo IRB**

The Principal Investigator and/or Investigators will report, as soon as possible, but no later than 5 working days after first learning of the problem/event, to the Mayo Clinic IRB any UPIRTSOs and Non-UPIRTSOs according to the Mayo Clinic IRB Policy and Procedures.

Documentation of adverse events will include the following information collected in the adverse event section of the case report form (and entered into the research database):

- Subject's name:
- Medical record number:
- Disease:
- The date the adverse event occurred:
- Description of the adverse event:
- Relationship of the adverse event to the research:
- If the adverse event was expected:
- The severity of the adverse event (defined by a severity scale):
- If any intervention was necessary:
- Resolution (was the incident resolved spontaneously, or after discontinuing treatment):
- Date of Resolution:

The Principal Investigator and/or Investigators will review all adverse event reports to determine if specific reports need to be made to the IRB, FDA and Actelion. The Principal Investigator and/or Investigators will sign and date the adverse event report when it is reviewed. For this protocol, only directly related SAEs/UPIRTSOs will be reported to the IRB.

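### The closing sentence of 8.3.1 limits IRB reporting to directly related events, an undefined term that conflicts with the section's opening duty and with the possibly-related threshold in 8.1

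*Combined protocol and SAP*

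**What the plan says.** Four parts of the combined protocol and SAP bear on which events the IRB hears about.

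- **8.1, UPIRTSO definition.** The term covers "Any unanticipated problem or adverse event that meets the following three criteria": serious, unanticipated and related. An event counts as related "if it is possibly related to the research procedures".
- **8.1, Adverse Event.** The investigator judges whether there is a reasonable possibility that the study drug caused the event. The result is "documented as either related or unrelated".
- **8.3.1, first and last sentences.** The first sentence requires reporting to the IRB of "any UPIRTSOs and Non-UPIRTSOs according to the Mayo Clinic IRB Policy and Procedures", as soon as possible and "no later than 5 working days after first learning of the problem/event". The last sentence says that, for this protocol, "only directly related SAEs/UPIRTSOs will be reported to the IRB".
- **8.2, 8.3 and 8.3.2, reporting to the funder.** Under 8.2, an SAE in the reporting period that is "considered to be at least possibly related to the study treatment or study participation should be recorded and reported to Actelion immediately". Sections 8.3 and 8.3.2 also set the threshold at possible relatedness.

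**The concern.** The first and last sentences of 8.3.1 cannot both be followed as they stand. The last one is worded as a study-specific restriction, so a coordinator could reasonably take it as the operative rule. It rests on a degree of relatedness that the protocol neither defines nor records, and that appears stricter than the one in the protocol's own UPIRTSO definition.

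What is at stake is oversight of participant safety. Estimation, error rates and the efficacy analysis are not touched. The trial has one arm, is open label and has no interim analysis (7.2). Section 8.6 makes the Principal Investigator responsible for overseeing safety, and section 8 sets up no independent monitoring board. In that setting the IRB is an important outside reader of serious events, and the rule for what it receives should be unambiguous.

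**Working it through.** No arithmetic applies and the plan states no figure to reproduce. The check is a comparison of the reporting rules.

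**Step 1: is there a recorded category for direct relatedness?** No. The term appears as a reporting criterion only in the last sentence of 8.3.1 and is not explained there. The causality record in 8.1 has two values, related and unrelated. The case report form items listed in 8.3.1 include relationship to the research but give no grading. Two investigators could therefore apply the closing rule differently to the same event, and the data would not show which reading was used.

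**Step 2: what does each rule do with a given event?** The closing sentence can be read in two ways. In reading A, *directly related* qualifies both SAEs and UPIRTSOs. In reading B, it qualifies SAEs only. The table is confined to medical events that meet the SAE definition.

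| Type of SAE | IRB: opening sentence | IRB: closing sentence, reading A | IRB: closing sentence, reading B | Funder (8.2, 8.3, 8.3.2) |
|---|---|---|---|---|
| UPIRTSO, directly related | Reported | Reported | Reported | Reported |
| UPIRTSO, possibly but not directly related | Reported | **Not reported** | Reported | Reported |
| Not a UPIRTSO, directly related | According to IRB policy | Reported | Reported | Reported |
| Not a UPIRTSO, possibly but not directly related | According to IRB policy | **Not reported** | **Not reported** | Reported |

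**Step 3: what follows.**

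- Under reading A, an event can meet the 8.1 definition of a UPIRTSO in full and still be kept from the IRB by the closing sentence. This contradicts the opening sentence directly.
- Under reading B, every UPIRTSO is reported. The gap shrinks to SAEs that are possibly but not directly related and are not UPIRTSOs, for example because the risk is already described in the protocol. Section 1.6 lists non-melanoma skin cancer and eye injury among the known risks. For skin cancer it adds that the absolute risk attributable to the product itself is not established. A case classed as serious could therefore be judged possibly related without being called directly related.
- Under either reading, the closing sentence sends the IRB fewer possibly related SAEs than the funder receives.

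**Step 4: can the gap be sized?** No. The protocol gives no expected rate of SAEs in this population and no expected split between possible and direct relatedness. The IRB policy to which the opening sentence defers is not part of the documents.

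**The case against.** The strongest reply is that the opening sentence of 8.3.1 is a mandatory, time-limited duty covering every UPIRTSO, and that by the 8.1 definition this already includes possibly related events. A site following it would report. The text does not say which sentence governs, and reading B keeps all UPIRTSOs in. This stands. A reader might infer that possibly related serious events would certainly be withheld from the IRB, but the documents support only that they could be.

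A reader might also infer that most qualifying events would fall outside the closing rule, because there is no control arm and no earlier efficacy research in this disease (1.4). The documents do not support that. Section 1.6 describes known risks from other uses, and local effects such as application-site dermatitis or accidental eye exposure are events for which direct attribution is plausible without a comparator.

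Third, the IRB is not the only outside check. Under 8.3.2 the funder's safety unit passes information to health authorities, and section 10 provides for monitoring, audit and inspection. The threshold for the funder is tied to marketed-product reporting, so a difference between the two routes is not in itself an error. This also stands, but none of these routes is stated to give the IRB the event report.

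Finally, all adverse events are recorded (8.2), and the investigators review every report to decide what goes to the IRB (8.3.1). That is true, but the closing sentence is the rule they are given for that decision, and it is the one that cannot be applied consistently.

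**Conclusion.** The inconsistency is real. The closing sentence of 8.3.1 uses an undefined term that matches no recorded causality category, and it conflicts with the section's opening duty. Read as covering both kinds of event, it also conflicts with the possibly-related threshold in the UPIRTSO definition. If it is followed, a serious event judged possibly but not directly related could reach the funder and not the IRB.

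This conclusion assumes that the closing sentence is taken as the study-specific rule. How wide the gap is depends on whether the restriction attaches to UPIRTSOs as well as SAEs, and on an IRB policy that is not available here. Its size cannot be determined from the documents. The matter is worth correcting before enrolment because it concerns participant protection. It has no bearing on the LPPAI analysis or the sample size.

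**What to change.** Delete the closing sentence of 8.3.1 and put one rule in its place, for example: *All UPIRTSOs, and all SAEs judged at least possibly related to study treatment or to taking part in the study, will be reported to the IRB within 5 working days of the study team learning of them; other events will be reported as IRB policy requires.* Check the wording against the IRB policy itself. In the Adverse Event part of 8.1, state that an event recorded as related includes one judged possibly related, so that the recorded category maps onto the reporting rule.

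Changing only the word *directly* to *possibly* would not be enough. The restriction to *only* such events would still conflict with the opening duty on Non-UPIRTSOs, and read literally it could leave out events judged definitely related.

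The cost is a short protocol edit and possibly a few more IRB reports among 20 patients. Data collection and analysis do not change.
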